9.2 SAFETY ANALYSIS

The All-Patients-as-Treated (APaT) population will be employed for safety analyses. The secondary safety endpoints are the Grade 3 and 4 adverse event and the all adverse events graded from 1 to 5. Both secondary endpoints are dichotomous and will be summarized using frequency (in %). In addition, the 95% confidence intervals (CI's) will be calculated using the exact method, i.e. the binomial distribution method. We expect to reach 13% of Grade 3 and 4 adverse event and 58.9% of all Graded Adverse events, similar to those reported in the Checkmate 141 study.

9.3 SAMPLE SIZE

We expect that the use of the Nivolumab-based adjuvant therapy will improve 2 year disease-free survival (DFS) by 20%. The optimal single-arm two-stage design with time-to-event endpoints(Kwak & Jung, 2014) will be used to test the null hypothesis that DFS at 2 years $\leq 33\%$, which is based on the historic data, versus the alternative that DFS at 2 years $\geq 53\%$, by a one-sided, one-sample log-rank test with the power of 80% at a 5% significance level. After 17 patients are entered in the first stage, the trial will be terminated if the test statistic at stage 1 > 0.76 . If the trial goes on to the second stage, a total of 39 patients will be studied. We reject the null hypothesis if the test statistic at stage 2 > -1.62 . Considering a drop-out rate of 10%, a total of 39 patients are needed for this study.

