The primary objective is to assess efficacy of Nivolumab in these patients who have been subjected to multiple modalities of treatment using DFS at 2-years. Each subject will be assessed to evaluate for potential new or worsening AEs as specified in the Trial Flow Chart and more frequently if clinically indicated. Adverse events will be graded and recorded throughout the study and during the follow-up period according to NCI CTCAE Version 5.0. Toxicities will be characterized in terms regarding seriousness, causality, toxicity grading, and action taken with regard to trial treatment.

Sample Size Justification:

We expect that the use of the Nivolumab-based adjuvant therapy will improve 2 year disease-free survival (DFS) by 20%. The optimal single-arm two-stage design with time-to-event endpoints will be used to test the null hypothesis that DFS at 2 years $\leq 33\%$, which is based on historic data, versus the alternative that DFS at 2 years $\geq 53\%$, by a one-sided, one-sample log-rank test with the power of 80% at a 5% significance level. After 17 patients are entered in the first stage, the trial will be temporarily suspended to new enrollment to allow for an interim statistical analysis. The trial will be terminated if the test statistic at stage 1 > 0.76 .

If the trial goes on to the second stage, a total of 35 patients will be studied. We reject the null hypothesis if the test statistic at stage 2 > -1.62 . Considering a drop-out rate of 10%, a total of 39 patients are expected to be required for this study.

Efficacy Analyses:

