9.4 ACCRUAL RATE

At the University of Cincinnati, we see approximately 300-350 new cases of HNSCC per year. Of those, approximately 100-150 stage III/IV HNSCC are treated with radiation +/- chemotherapy. Our institution conducted a retrospective analysis and identified twenty-eight patients over a 1-year period that were initially treated with definitive concurrent CRT or RT alone who subsequently developed local recurrence and required salvage resection. Based on this we expect to accrue approximately 1-2

patients per month at UC. From the similar consideration as UC, we expect that the accrual rates would be 2 patients per month at Karmanos Cancer Institute. That will yield a combined 2-institution effective accrual rate of 3-4 patients per month. Thus we expect enrollment for this phase II study to be completed within 10-13 months based on 39 patients.

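### Under the usual one-sample log-rank statistic, the final cut-off of -1.62 has a size of about 4% rather than 5%; the statistic should be defined and the cut-off calibrated to the real interim timing, accrual and follow-up

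*Combined protocol and SAP*

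**What the plan says.** Section 9.3 sets out a two-stage single-arm design for 2-year DFS. The null is 33% and the alternative 53%, tested "by a one-sided, one-sample log-rank test with the power of 80% at a 5% significance level". The interim look comes in 9.3 with "After 17 patients are entered in the first stage", and "the trial will be terminated if the test statistic at stage 1 > 0.76". At the end, "We reject the null hypothesis if the test statistic at stage 2 > -1.62". A published two-stage time-to-event design is cited. The plan does not print the formula of the statistic, its variance estimator, the shape of the null survival curve, or the accrual and follow-up from which the cut-offs were derived.

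Other sections bear on the operating characteristics:

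- **Final sample size.** The synopsis says "If the trial goes on to the second stage, a total of 35 patients will be studied". Section 9.3 gives 39 for the same stage. Both reach 39 after allowing for 10% drop-out.
- **Accrual.** Section 9.4: "That will yield a combined 2-institution effective accrual rate of 3-4 patients per month".
- **Interim pause.** The synopsis suspends enrolment temporarily for the interim analysis, for an unstated time. Section 9.3 does not mention this.
- **Follow-up.** The synopsis (Efficacy Analyses) censors two years after the last patient is enrolled. Section 7.5.8 follows patients for relapse for 2 years in total. Section 7.7.4 allows up to 2 years of follow-up visits after the last dose.

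**The concern.** A cut-off of -1.62 comes from a normal approximation. The final analysis expects only about 25 to 29 events under the null, and there the standard statistic is not close to normal in the tail that matters. A result that favours the drug is one in which E is large relative to O. The same large E sits in the denominator and pulls the statistic back towards zero, so the benefit tail is shorter than the normal tail and the cut-off is harder to cross than 5% implies.

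This is the trial's only formal efficacy test, the sample is small, and section 4.6 says subjects are not replaced. If part of the accepted type I error is unused, a borderline effective result can be declared negative for no gain in protection. The stated 80% power also cannot be checked, because it depends on interim timing and follow-up that the plan leaves open.

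**Working it through.** **Inputs from the plan.** DFS at 2 years of 0.33 and 0.53; 17 then 35 patients (39 with drop-out); cut-offs 0.76 and -1.62; 3-4 entries per month; censoring 24 months after the last entry.

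**Assumptions.** Exponential DFS; statistic (O-E)/sqrt(E), where O is observed events and E is the sum of null cumulative hazards; low values favour the drug. The last is consistent with the stage 1 rule, which stops for high values.

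**Hazards.** Null: -ln(0.33)/2 = 0.554 per year (0.0462 per month). Alternative: -ln(0.53)/2 = 0.317 per year. Hazard ratio 0.317/0.554 = 0.573.

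**Sample size.** 35/0.9 = 38.9, so 39 is reproduced.

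**Information at the interim.** If the look is at the 17th entry, patients have 0 to 16/3 = 5.3 months of exposure at 3 per month, 2.67 on average. Expected null events are at most 17 x 2.67 x 0.0462 = 2.1. At 4 per month they are at most 17 x 2.0 x 0.0462 = 1.6. That is about 6-8% of the final information.

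**Normal theory, N = 35.** With no interim, the size is the normal probability below -1.62, or 5.26%. With stage 1 stopping above 0.76:

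- at 3, 3.5 and 4 per month, size is 4.82, 4.78 and 4.75%, and power is 78.4, 77.6 and 76.9%;
- at about 26 per year, size is 4.9% and power 80.1%. The printed design therefore agrees with its claims at an accrual slower than section 9.4 states (36-48 per year).

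**Simulation, N = 35** (500,000 to 1,000,000 trials per row, entries uniform over the accrual period, size / power in %):

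| Setting | sqrt(E), -1.62 | sqrt(E), -1.53 | sqrt((O+E)/2) at final test, -1.62 |
|---|---|---|---|
| 3 per month, look at 17th entry | 3.9 / 78.6 | 4.8 / 80.8 | 5.1 / 81.3 |
| 3.5 per month, same | 3.9 / 77.6 | 4.8 / 79.8 | 5.1 / 80.4 |
| 4 per month, same | 3.9 / 76.9 | 4.8 / 79.1 | 5.0 / 79.7 |
| 3.5 per month, each patient capped at 2 years | 4.0 / 74.1 | 4.8 / 76.6 | 5.2 / 77.5 |
| 3.5 per month, look read 6 months after 17th entry | 4.2 / 81.3 | 5.1 / 83.6 | 5.4 / 84.2 |
| 3.5 per month, look read 24 months after 17th entry | 4.3 / 82.2 | 5.3 / 84.6 | 5.6 / 85.2 |

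With Weibull shapes 0.7 and 1.3 in place of the exponential (3.5 per month), the sqrt(E) size at -1.62 is 4.05% and 3.8%. A separate run of 100,000 trials per cell covered N = 35 and 39, immediate looks and pauses of 2-6 months, with and without the 2-year cap. It put the size at about 3.7-4.2%.

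**Where the size goes (3.5 per month).** The early stop takes 5.26 - 4.78 = 0.48 points. The non-normal tail takes a further 4.78 - 3.94 = 0.84 points.

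**Where the power goes (3.5 per month).** Normal-theory and simulated power with the look agree at 77.6%, so the variance does not explain the gap to 80%. Without the look, simulated power is 82.2%, so the early look costs 82.2 - 77.6 = 4.6 points.

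**Enrolment pause.** Taking the synopsis suspension as 2 months (assumed), sqrt(E) with -1.62 gives 79.3-81.3% power at 3-4 per month. With 3 months (assumed) it gives 80.2-81.9%.

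**N = 39.** With 10% loss, at 3.5 per month, sqrt(E) power with -1.62 is 79.6%, or 76.1% with the 2-year cap.

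**The case against.** The strongest reply is that nothing stated is violated. A size of 3.9% respects a 5% level, and conservatism is not an error. That stands: a reader might infer that the test is invalid or that type I error is inflated, and neither follows.

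Nor do the documents support calling 3.9% the true size without qualification. With no formula printed, the size at -1.62 depends on the variance: about 3.9% with E, 5.0-5.2% with (O+E)/2 and 6.3-6.4% with O (3-4 per month, look at the 17th entry). The order is expected, because when O < E we have O < (O+E)/2 < E, so E gives the least extreme value. If the sponsor already intends (O+E)/2, the conservatism disappears. The omission then remains the defect.

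A reader might also blame the variance for the missed 80%. The working shows otherwise, and a 2-3 month pause brings power with sqrt(E) to about 79-82% at 35 patients. With 39 patients and 10% loss it is close to target unless follow-up is capped.

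Finally, it is tempting to switch to (O+E)/2, keep 1.62 and regard size and power as restored at no cost. The table does not support this. Size reaches 5.2% with the cap and 5.4-5.6% with a later look, and power under the cap is still only 77.5%.

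It is also fair to say that the printed direction and the 35/39 conflict matter more than one point of conservatism. Read literally and ignoring futility, rejecting above -1.62 rejects about 96% of null trials.

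**Conclusion.** The point holds conditionally. With (O-E)/sqrt(E) and rejection for low values, -1.62 gives a one-sided size of about 3.7-4.2%, so roughly 0.8 to 1.3 points of the stated 5% are unused. This is stable across the accrual rates, the two sample sizes, interim delays up to 6 months, and the follow-up and survival shapes tried. Recalibration is worth about 2-3 points of power.

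The 80% claim is neither confirmed nor clearly refuted. At 35 patients and 3-4 per month, power runs from about 73-77% if relapse follow-up is capped at 2 years per patient, through 77-79% with an immediate look, to 79-82% with a 2-3 month pause. The plan does not say which of these applies.

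The change should be made because it is cheap and concerns the primary decision rule. It is a matter of efficiency and specification, not of a false-positive risk. The conclusion rests on the assumed formula and, for the power figures, on exponential DFS.

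**What to change.** In section 9.3 and in the synopsis:

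1. Write out the statistic and its variance, and use the same form at both looks.
2. Correct the final rule so that the null is rejected for values below the cut-off.
3. Reconcile 35 with 39 as the number analysed at stage 2.
4. State the null survival shape, the accrual rate, when the interim is read, how long enrolment is suspended, and one follow-up rule consistent with sections 7.5.8 and 7.7.4 and the synopsis.
5. Replace -1.62 with a cut-off calibrated by simulation to a size of at most 5% under those conditions. With sqrt(E) this is about -1.53. It must be recomputed for the actual interim timing, since -1.53 itself gives 5.1% if the look is read 6 months after the 17th entry.
6. Report the simulated size and power in place of the unverified 5% and 80%.

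Do not simply substitute (O+E)/2 while keeping 1.62. If that variance is preferred, its cut-off needs the same calibration.

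The cost is a wording amendment and a short simulation, with no extra patients, visits or data. The downside is that the actual size rises towards the 5% already claimed. Because the new cut-off is easier to cross, it should be fixed before outcome data are examined.

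### The final rejection rule points the wrong way: as written, a drug with no benefit usually passes, and on the scale stage 1 implies an effective one usually fails

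*Combined protocol and SAP*

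**What the plan says.** Section 9.3 and the synopsis paragraph on sample size describe an optimal two-stage single-arm design. The null is a 2-year DFS of at most 33% and the alternative at least 53%, tested "by a one-sided, one-sample log-rank test with the power of 80% at a 5% significance level". The interim comes once 17 patients have entered, and "the trial will be terminated if the test statistic at stage 1 > 0.76". The final rule is "We reject the null hypothesis if the test statistic at stage 2 > -1.62". The synopsis uses the same two inequalities, so neither place corrects the other.

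The plan does not write out the test statistic, its sign or its variance. The other efficacy text (sections 9.1, 9.5.1 and 9.6.1) covers the DFS definition and Kaplan-Meier summaries and gives no other test of the primary hypothesis.

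The two places differ on the stage 2 total. The synopsis has "If the trial goes on to the second stage, a total of 35 patients will be studied", while section 9.3 prints 39 at that point.

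**The concern.** The two boundaries cannot both be right. Ending the trial on a large positive stage 1 value makes sense only if positive means more events than the null predicts. Benefit then shows as a negative value, and a one-sided test must reject in the lower tail. The final rule instead rejects for everything above -1.62. That includes zero (exactly as the null predicts) and positive values (worse than the null).

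This rule decides whether adjuvant nivolumab is called effective. If the direction is put right only after results are known, the correction will look like a change of the success criterion, however obvious the slip.

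**Working it through.** **Inputs from the plan.** 2-year DFS 33% and 53%; one-sided 5%; power 80%; stage 1 size 17; boundaries 0.76 and -1.62 (section 9.3 and synopsis). Stage 2 total 35 (synopsis); 35/(1 - 0.10) = 38.9, rounded up to 39, so 35 is the design size and 39 the enrolment target. Accrual 3-4 per month (section 9.4). The study ends two years after the last enrolment (synopsis, efficacy analyses), but section 7.5.8 limits relapse follow-up to 2 years in total. Both follow-up readings were run.

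**Assumptions.** Exponential DFS, evenly spread accrual, interim at entry of patient 17, and the usual one-sample log-rank form W = (O - E)/√E, where O is observed events and E is events expected under the null.

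**Hazards.** Null: -ln(0.33)/24 = 0.0462 per month. Alternative: -ln(0.53)/24 = 0.0265 per month. Hazard ratio 0.573.

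**Where W should fall if the drug works.** With 35 patients each followed 2 years at 53% DFS:
- O = 35 × 0.47 = 16.45
- E = 16.45/0.573 = 28.7
- W ≈ (16.45 - 28.7)/√28.7 ≈ -2.3

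The alternative is centred near -2.3, below -1.62, which is the region where the written rule does not reject.

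**Reproducing the stated design (normal approximation).** Under the null, W1 and W2 are treated as bivariate normal with correlation √(stage 1 information/final information), about 0.25-0.30 at 3-4 per month.
- P(W1 ≤ 0.76) = 0.776
- P(W1 ≤ 0.76 and W2 < -1.62) = 0.048, matching the stated 5%
- Power with the < rule: 0.74-0.84, depending on the follow-up reading and variance formula, bracketing the stated 80%

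**The rule as written (normal approximation).**
- Null: 0.776 - 0.048 = 0.728
- Stage 2 rule alone, ignoring stage 1: P(Z > -1.62) = 0.947
- Alternative: 0.12-0.22

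**Simulation (35 patients, 3-4 per month).**

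| Follow-up | Rule | Success at DFS 33% | Success at DFS 53% |
|---|---|---|---|
| 24 months after last entry | as written (>) | 69-79% | 14-16% |
| 24 months after last entry | reversed (<) | about 4% | 77-79% |
| 24 months per patient | as written (>) | 69-79% | 18-20% |
| 24 months per patient | reversed (<) | about 4% | 73-75% |

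**Opposite sign (positive = benefit).** Stage 1 would then stop trials that are going well. With that stop, the written rule passes a null drug in about 73-82% of trials; the stage 2 rule alone does so in about 93-95%. At DFS 53% it declares success in about 59-70%.

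**Sensitivity.** With 39 patients instead of 35 (4 per month, 24 months per patient), the written rule gives 78.5% and 16%, and the reversed rule 4% and 79%. In the normal approximation, accrual of 1.5-4 per month and follow-up of 1-2 years do not change the conclusion.

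**The case against.** The strongest objection is that the sign is inferred. The plan does not define the statistic and does not call the stage 1 rule a futility stop. That stands, and it limits one half of the point: that an effective drug usually fails depends on positive meaning excess events. On the opposite scale the written rule would succeed in 59-70% of trials at DFS 53%. The other half, that a null drug usually passes, holds under either sign. Only the observed-minus-expected sign makes stage 1 a futility rule and approximately returns 5% and 80%.

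It can also be said that a statistician who knows the method would spot the slip, and that the planned Kaplan-Meier estimate of 2-year DFS with its confidence interval would expose an absurd conclusion. Both make literal use less likely. Neither replaces a pre-specified decision rule.

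Finally, dividing by √E is an assumption, since the plan names no variance estimator. The direction of the inequality does not depend on that choice.

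**Conclusion.** The rule is wrong as written and must be corrected. Literal use gives a type I error of about 69-79% instead of 5%. On the scale that stage 1 implies, success is declared in only 14-20% of trials of a drug with the targeted effect, so it fails in 80-86%. Reversing one inequality brings the type I error to about 4-5% and simulated power to 73-79%. The values 0.76 and 1.62 are therefore consistent with the design, and only the stage 2 direction is at fault.

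The exact percentages rest on exponential DFS, accrual at the planned rate and an interim at the 17th entry. The contradiction between the two boundaries needs none of these assumptions.

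**What to change.** In section 9.3 and in the synopsis, state that the null is rejected if the stage 2 statistic is below -1.62, the trial having continued past stage 1. Add one sentence defining the statistic, for example (O - E)/√E with negative values favouring nivolumab, after confirming from the sponsor's design calculation that this is the form that produced 0.76 and -1.62. In the same amendment, make the stage 2 total in section 9.3 agree with the synopsis (35 for the design, 39 enrolled).

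The cost is a text amendment in two places, with no change to sample size, data collection or patient procedures. It should be made and dated before the stage 2 statistic is computed.

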9.4 ACCRUAL RATE

At the University of Cincinnati, we see approximately 300-350 new cases of HNSCC per year. Of those, approximately 100-150 stage III/IV HNSCC are treated with radiation +/- chemotherapy. Our institution conducted a retrospective analysis and identified twenty-eight patients over a 1-year period that were initially treated with definitive concurrent CRT or RT alone who subsequently developed local recurrence and required salvage resection. Based on this we expect to accrue approximately 1-2

patients per month at UC. From the similar consideration as UC, we expect that the accrual rates would be 2 patients per month at Karmanos Cancer Institute. That will yield a combined 2-institution effective accrual rate of 3-4 patients per month. Thus we expect enrollment for this phase II study to be completed within 10-13 months based on 39 patients.

9.5 STATISTICAL ANALYSIS PLAN FOR ENDPOINTS

9.5.1 EFFICACY ENDPOINTS

Primary and secondary endpoints of efficacy are 2-year and 1-year DFS, respectively. DFS will be defined as the duration from the time of treatment allocation to the time of discovery of the first evidence after treatment of any tumor (local, regional, metastatic, or second primary) or death from any cause.

9.5.2 SAFETY ENDPOINTS

The first secondary safety endpoint of study will be to determine if adjuvant Nivolumab for a minimum of 6 months has similar Grade 3 and 4 adverse event rates as the Checkmate -141 trial.

The second secondary safety endpoint of study will be to determine if adjuvant Nivolumab for a minimum of 6 months has similar all grade adverse event rates as the Checkmate-141 trial. Both the primary and secondary adverse events will be summarized by frequency in % and its CI's will be calculated using a binomial distribution. The exact test or the binomial test will be used to test the proposed hypotheses specified in 9.3.

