9.6.2 SAFETY ANALYSIS

Descriptive statistics will be provided for safety endpoints. In particular, the dichotomous primary and secondary endpoints will be summarized using frequency (in %) with a 95% CI calculated using a binomial distribution. The binomial test (or the Exact test) will be used to test the hypothesis proposed in 9.3.

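### The safety test points to a hypothesis that Section 9.3 does not contain, and a binomial test against the CheckMate-141 rates could not show that the rates are similar

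*Combined protocol and SAP*

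**What the plan says.** Section 9.5.2 sets two secondary safety endpoints. Each is to determine whether adjuvant nivolumab has an adverse event rate similar to that in CheckMate-141, one for Grade 3 and 4 and one for all grades. It plans frequencies with binomial confidence intervals and then adds: "The exact test or the binomial test will be used to test the proposed hypotheses specified in 9.3". Section 9.6.2 says the same: "The binomial test (or the Exact test) will be used to test the hypothesis proposed in 9.3". Both sections also use the word primary for safety endpoints, although the synopsis and Section 9.2 list them only as secondary.

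Section 9.2 defines the endpoints: "The secondary safety endpoints are the Grade 3 and 4 adverse event and the all adverse events graded from 1 to 5". It gives expected rates of 13% and 58.9%, and plans exact 95% confidence intervals in the all-patients-as-treated population.

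Section 9.3, to which both sentences refer, states a "null hypothesis that DFS at 2 years $\leq 33\%$, which is based on the historic data", against an alternative of at least 53%, to be tested "by a one-sided, one-sample log-rank test with the power of 80% at a 5% significance level". The rest of the section covers the two-stage cut-offs and the sample size. It does not mention safety.

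**The concern.** The safety test cannot be run as written, because the hypothesis it refers to does not exist. Whoever does the analysis would have to choose the null rate, the direction and the significance level, possibly after seeing the data.

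Correcting the section number would not solve this. The stated aim is to determine whether the rates are similar, and the natural null values are 13% and 58.9%. In a test of difference from those values, the result that looks favourable is a failure to reject. In a trial of this size that is likely even when toxicity is clearly higher than the benchmark. What is at stake is a secondary safety conclusion that the data could not support.

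**Working it through.** **Comparing the sections.** Sections 9.5.2 and 9.6.2 order a binomial or exact test of a hypothesis in 9.3. Section 9.3 has one hypothesis, on 2-year DFS, with its own test, power and level. Sections 9.2, 9.5.2 and 9.6.2 and the synopsis give expected safety rates and the word similar, but no null, alternative, margin, direction, level or power for safety.

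**The plan's own figure.** The only sample size is for DFS. The synopsis gives 35 patients at the second stage and 10% drop-out: 35/0.9 = 38.9, rounded up to 39. This reproduces the stated 39, but it carries no information about power for safety.

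**Inputs for the safety check.**
- n = 39 treated (Section 9.3), with n = 35 as the lower case. The safety population is treated patients, so 39 is the most favourable figure.
- Null rates of 13% and 58.9% (Section 9.2).
- One-sided 5% level. This is an assumption, because the documents give no level for safety.

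**Rejection threshold for 13%.** Find the smallest k with P(X ≥ k) ≤ 0.05, where X ~ Binomial(39, 0.13).
- P(X ≥ 9) = 0.059, so 9 of 39 (23.1%) does not reject.
- P(X ≥ 10) = 0.025, so the threshold is 10 of 39 (25.6%).

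**Chance of reaching 10 or more of 39 for a given true rate.**

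| True Grade 3 and 4 rate | Test rejects | Test misses |
|---|---|---|
| 20% | 24% | 76% |
| 25% | 52% | 48% |
| 26% (2 × 13%) | 58% | 42% |
| 30% | 78% | 22% |

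With n = 35 the threshold is 9 patients (25.7%), and the chance of rejecting at a true 26% is again 58%. A two-sided 5% test with n = 39 also fails to reject at 9 events: it does not reject for 1 to 9 events (2.6% to 23.1%).

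**The all-grade rate.** Against 58.9% with n = 39, the one-sided threshold is 29 patients (74.4%). A true rate of 70% is flagged 35% of the time. The two-sided test does not reject for 17 to 29 events (43.6% to 74.4%) and flags a true 70% 22% of the time.

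**What the planned intervals would show (exact, 95%).**
- 5/39 = 12.8%: 4.3% to 27.4%.
- 9/39 = 23.1%: 11.1% to 39.3%. This does not reject 13%, yet the interval extends to three times the benchmark.
- 23/39 = 59.0%: 42.1% to 74.4%.
- With n = 35: 5/35 = 14.3%, 4.8% to 30.3%; 21/35 = 60.0%, 42.1% to 76.1%.

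**What a formal claim would need.** Suppose the aim were to show that the rate is below the benchmark plus a margin, with the true rate equal to the benchmark and a one-sided 5% exact test. The documents give no margin, so a range is shown.

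| Margin (points) | Power at n = 39, 13% rate | N for 80% power, 13% rate | Power at n = 39, 58.9% rate | N for 80% power, 58.9% rate |
|---|---|---|---|---|
| 10 | 42% | 107 | 31% | 153 |
| 15 | 60% | 53 | 56% | 68 |
| 20 | 87% | 33 | 79% | 40 |

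For the 13% rate, 39 patients give 80% power only at the widest margin shown, which means ruling out 33%. For the 58.9% rate they fall just short even there.

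**The case against.** The strongest reply is that this is a wrong cross-reference in a plan that already does the right thing. Exact 95% intervals are planned, no trial decision depends on the safety test, and nowhere does the text say that non-significance will be read as similarity. An observed rate of about double the benchmark (10 of 39) would be flagged, and the one-sided 5% level is not the plan's.

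Most of this is fair, and it limits the point to the wording of secondary endpoints. It does not rescue the test. Section 9.5.2 still sets out to determine similarity and names a test as the tool. The intervals do the useful work without it.

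Two stronger readings are tempting, and the documents do not support either.

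First, a reader might infer that the plan names a second, binomial test for DFS that ignores censoring. Both sentences stand under safety headings and follow text on safety frequencies. The efficacy sections name no such test, and 9.3 assigns DFS to the log-rank test.

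Second, a reader might infer that leaving Grade 5 out of the severe endpoint invalidates the comparison, or that a toxic death lowers the severe rate. Section 2.3 describes the 13% benchmark as Grade 3 and 4 too, so the definitions match. The denominator is all treated patients, so an uncounted fatal event leaves the rate unchanged. Section 8.8 records each change of grade, so an event that passed through Grade 3 or 4 has that grade on record. Fatal events also count in the all-grade endpoint and in the tables by grade (Section 9.6.3). What remains is small: a patient whose only severe record is Grade 5 would not appear in the Grade 3 and 4 rate.

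**Conclusion.** The point holds. Sections 9.5.2 and 9.6.2 order a test of a safety hypothesis that is stated neither in 9.3 nor elsewhere in the supplied text. If the test is run against 13% or 58.9%, failing to reject would not show that the rates are similar. The size depends on 39 treated patients and the assumed one-sided 5% level, but the conclusion does not: it is the same with 35 patients or with a two-sided test. The DFS design and the descriptive comparison by rate and exact interval are unaffected. The change should be made, but it concerns secondary endpoints only.

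**What to change.** - Delete the binomial-test sentences in Sections 9.5.2 and 9.6.2, and remove the word primary where those sections apply it to safety endpoints.
- In Section 9.5.2 and in the synopsis list of secondary endpoints, replace the aim of determining similar rates with estimating the two rates with exact 95% confidence intervals. State that the CheckMate-141 rates are descriptive context and that similarity is not tested.
- As a minor reporting addition, show worst grade 3 to 5 per patient beside the Grade 3 and 4 rate. Keep Grade 3 and 4 for the like-for-like comparison.

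The cost is a wording change and one table row, with no change to design or sample size. The downside is that the trial makes no formal claim of similarity. If the sponsor wants one, the null rate, margin, direction and level must be stated for each endpoint before the data are seen, and 39 patients would support only a wide margin.
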